10.16.5 Patient Expectations Questionnaire at Baseline (PEQ-BL)

Review Copy Do Not Use Without Permission

[figure not shown]
10.16.6 Patient experience and satisfaction follow-up questionnaire (PESQ-FU)

[figure not shown]

Review Copy Do Not Use Without

10.16.7 Patient experience and satisfaction end-of-treatment questionnaire (PESQ-EOT)

[figure not shown]

Page 2 of 4

[figure not shown]
PESQ-EOT ©Sanofi Genzyme, 2018-2021. All Rights Reserved.
PESQ-EOT_English-US-v4_Sept.-14-2021

13. What are the main reasons that make you prefer this **Injection method**?

Page 3 of 4

PESQ-EOT ©Sanofi Genzyme, 2018-2021. All Rights Reserved.
PESQ-EOT_English-US-v4_Sept.-14-2021

Review Copy Do

Page 4 of 4

PESQ-EOT ©Sanofi Genzyme, 2018-2021. All Rights Reserved.
PESQ-EOT_English-US-v4_Sept.-14-2021

10.16.8 Patient's Assessment of Treatment questionnaire (PAT)

Patient's Assessment of Treatment Questionnaire (PAT)

10.16.9 Local Tolerability at Injection Site After Isatuximab Administration - Patient Assessment Using Diary

Patient Local Tolerability Questionnaire (PLTQ): At-home symptom diary: one page per date and per Event (symptom experienced)

Please note if you are having any severe symptoms, side effect, health issues or other concerns, please be sure to discuss these with your doctor or nurse as this questionnaire is not reviewed by your health care team.

Complete checklist on next page if any of pain, swelling, redness, itching, bruising, hardening, burning, cold sensation(s) or other symptoms at injection site experienced; use the scoring for severity and interference scales provided below:

Bring all pages of at-home symptom diary (Patient Local Tolerability Questionnaire) to next study visit

Use Scales below to complete Severity and Interference columns on next page

Severity (at its worst)	Interference (at its worst) with your usual or daily activities
0=None	0=Not at all
1=Mild	1=A little bit
2=Moderate	2=Somewhat
3=Severe	3=Quite a bit
4=Very severe	4=Very much

If none of the symptoms experienced (on form next page) please check box below:

No pain, swelling, redness, itching, bruising, hardening, burning, cold sensation(s), tenderness or other symptoms at injection site experienced.

Patient Local Tolerability Questionnaire (PLTQ): At-home symptom diary: one page per date and per Event (symptom experienced)

Complete below if any 1. Pain, 2. Swelling, 3. Redness, 4. Itching, 5. Bruising, 6. Hardening, 7. Burning,
8. Cold sensation(s) or 9. Warm sensation(s), 10. Tenderness or Other symptoms at injection site experienced; **SEEK
APPROPRIATE MEDICAL CARE/CONTACT YOUR NURSE/DOCTOR IMMEDIATELY IF ANY SEVERE SYMPTOMS OR CONCERNS**

Symptom (at its worst) :	Start date Time started (eg 8:23 AM or 0823) DD-MMM-YEAR (eg 25-MAY- 2021)	Stop Date Time stopped (eg 8:25 AM or 0823) DD-MMM-YEAR (eg 25-MAY- 2021)	Start Time HH-mm	Stop Time HH-mm	Severity (at worst) : 0=Not at all 1=Mild 2=Moderate 3=Severe 4=Very severe	Interference (at worst) 0=Not at all 1=A little 2=Somewhat 3=Quite a bit 4=Very much
1. Pain at injection site						
2. Swelling at injection site						
3. Redness at injection site						
4. Itching at injection site						
5. Bruising at injection site						
6. Hardening at injection site						
7. Burning at injection site						
8. Cold sensation(s) at injection site						
9. Warm sensation(s) at injection site						
10. Tenderness at injection site						
11. Other injection site symptom, specify						
12. Other injection site symptom, specify						

PLTQ ©Sanofi Genzyme, 2018, 2019, 2020. All Rights Reserved.

PLTQ _ English-US –v4.nov-2-2020

Page 2

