u Adverse event/Serious AE reporting: All AEs, including AEs of new onset as well as worsening of baseline signs and symptoms are to be reported from the signing of the informed consent to 30 days following the last administration of any study treatment. After the 30-day follow-up, all ongoing related AEs or new related AEs, and all ongoing SAEs regardless of causal relationship are to be followed up to resolution or stabilization. In addition, second primary malignancies newly diagnosed during the entire study, including the post-treatment period, should be reported as AEs or SAEs, regardless of their causal relationship and followed up until resolution or stabilization. Severity will be graded according to NCI-CTCAE v5.0.

v Participants will stay at the site after isatuximab administration for at least 4 hours on Cycle 1/D1 in both SC and IV arms, 1 hour after the end of injection for the following Cycle 1 administrations (SC arm only) and per investigator judgement subsequently, if not longer for any other reason (eg, PK sampling) and will be monitored closely for IRs and Injection site reactions (ISRs). The HCP will stay at least 30 minutes with the participant after the first at-home administration, and per clinical judgement for the subsequent at-home administrations.

w Local tolerability at injection site after isatuximab SC administration– patient assessment using diary: A participant diary will be used in order to document any type of injection site reaction beyond clinic stay. Participants will fill out the questionnaire at home up to Cycle 9/Day 1. These data will support the Investigator to assess retrospectively the local tolerability at injection site and report ISRs, if needed ([Section 10.16](#)).

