6.4 STUDY INTERVENTION COMPLIANCE

6.4.1 Subcutaneous isatuximab at-home administration

Subcutaneous at-home administration will be performed by an HCP, after completing the questionnaire allowing for at-home administration (including vital signs and novel symptoms). For at-home administration, filling of this questionnaire should be recorded and in case at-home administration is not performed, reason should be collected.

Participants randomized in the SC arm will receive a participant diary. The purpose of the diary is to report potential ISRs during the first 9 cycles in the SC-arm.

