8.4.7 Assessment of local tolerability

Local tolerability at injection site after SC administration of isatuximab will be assessed during clinical stay using eCRF hourly (relative to the start of administration) for duration of 4 hours at Cycle 1/D1, 1 hour after the end of injection for the following Cycle 1 administrations and at end of injection from Cycle 2 onwards ([Section 1.3](#)). In case of at-home administration, for the first isatuximab injection performed at-home, an additional assessment should be performed 30 min after the end of the injection.

Table 19 - Summary of assessment timelines for local tolerability

On site administration	Cycle 1 Day 1: End of Injection (EoI), 1h, 2h, 3h, 4h Cycle 1 Day 8 & Cycle 1 Day 15: EoI, 1h Cycle 2 and subsequent cycles: EoI.
At-home administration	1st injection from Cycle 6: EoI, 30 min Rest of cycles: EoI.

Any swelling (unless it lasts longer than 24 hours) as a result of the injection of the isatuximab solution volume is not to be reported as an AE/ AESI.

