10.3.1 Definition of AE

AE definition

- An AE is any untoward medical occurrence in a participant or clinical study participant, temporally associated with the use of study intervention, whether or not considered related to the study intervention.
- NOTE: An AE can therefore be any unfavorable and unintended sign (including an abnormal laboratory finding), symptom, or disease (new or exacerbated) temporally associated with the use of study intervention.

Definition of unsolicited and solicited AE

- An unsolicited AE is an AE that was not solicited using a participant diary and that is communicated by a participant who has signed the informed consent. Unsolicited AEs include serious and non-serious AEs.
- Potential unsolicited AEs may be medically attended (ie, symptoms or illnesses requiring a hospitalization, or emergency room visit, or visit to/by a health care provider). The participants will be instructed to contact the site as soon as possible to report medically attended event(s), as well as any events that, though not medically attended, are of participant concern. Detailed information about reported unsolicited AEs will be collected by qualified site personnel and documented in the participant's records.
- Unsolicited AEs that are not medically attended nor perceived as a concern by participant will be collected during interview with the participants and by review of available medical records at the next visit.
- Solicited AEs are predefined local at the injection site and systemic events for which the participant is specifically questioned, and which are noted by the participants in their diary.

Events meeting the AE definition

- Any abnormal laboratory test results (hematology, clinical chemistry, or urinalysis) or other safety assessments (eg, ECG, radiological scans, vital signs measurements), including those that worsen from baseline, considered clinically significant in the medical and scientific judgment of the Investigator (ie, not related to progression of underlying disease), or more severe than expected for the participant's condition), eg:

- Leading to IMP discontinuation or modification of dosing, and/or,
- Fulfilling a seriousness criterion, and/or,
- Defined as an AESI.
- Exacerbation of a chronic or intermittent pre-existing condition including either an increase in frequency and/or intensity of the condition.

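### The injection-site diary tells participants that the care team does not review it, while the protocol has the investigator use it to report injection site reactions; its end date and Table 19 also conflict with other text

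*Protocol*

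**What the plan says.** **Diary review.** The form in Section 10.16.9 addresses participants with severe symptoms, side effects or other concerns as follows: "please be sure to discuss these with your doctor or nurse as this questionnaire is not reviewed by your health care team". The same form asks them to "Bring all pages of at-home symptom diary (Patient Local Tolerability Questionnaire) to next study visit". Footnote w of the schedule of activities (Section 1.3) introduces the diary to document any injection site reaction once the participant has left the clinic, and states: "These data will support the Investigator to assess retrospectively the local tolerability at injection site and report ISRs, if needed". Section 6.4.1 says: "The purpose of the diary is to report potential ISRs during the first 9 cycles in the SC-arm". Section 10.3.1 defines solicited adverse events as predefined local and systemic events on which the participant is questioned and "which are noted by the participants in their diary".

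**Diary end.** The schedule row and footnote w stop the diary at Cycle 9 Day 1. Section 6.4.1 and the injection-site row of Table 5 (Section 2.3.1) say that it covers the first nine cycles.

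**Investigator checks.** For Cycle 1 Day 1, Section 8.4.7 and footnote x ask for hourly assessment over 4 hours, counted from the start of administration. They then ask for a check "1 hour after the end of injection for the following Cycle 1 administrations", and from Cycle 2 a check at the end of injection. Table 19, in the same section, has for the later Cycle 1 injections only the line "Cycle 1 Day 8 & Cycle 1 Day 15: EoI, 1h" and then moves to Cycle 2.

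**The concern.** The diary is the only scheduled, structured record of what happens at the injection site after the participant goes home. A participant told that nobody reads it has less reason to complete it carefully, and site staff could take it for a questionnaire that bypasses them. Yet several rules in the protocol depend on information that arises after the on-site check:

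- Swelling caused by the injected volume is reportable only if it lasts more than 24 hours (Section 8.4.7, footnote x).
- A Grade 1 ISR during at-home dosing, or within 48 hours after it, changes where later injections are given (Table 15).
- An ISR of Grade 2 or higher is an AESI (Section 8.6.6), to be reported within 24 hours (Section 8.6.1).

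ISRs are also a listed secondary endpoint, in the SC arm only (Table 6). What is at stake is complete capture of mild and moderate late reactions to the new route of administration.

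**Working it through.** The plan gives no figure to reproduce. The check compares passages and counts scheduled SC injections.

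**1. Who reads the diary**

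| Place | What it implies |
|---|---|
| Diary form, 10.16.9 (warning sentence) | The care team does not review it |
| Diary form, 10.16.9 (return instruction) | Pages go to the site at the next visit |
| Footnote w | The investigator uses the data to assess tolerability and report ISRs |
| 6.4.1 and Table 5 | The diary exists to report possible ISRs |
| 10.3.1 | Diary entries are a source of solicited adverse events |

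The warning sentence conflicts with every other line, including one on the same form. It carries no qualifier such as between visits.

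**2. How far the on-site check reaches**

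- Cycle 1 Day 1: to 4 hours.
- Remaining Cycle 1 injections: to 1 hour after the end of injection (text of 8.4.7).
- Cycle 2 onwards: end of injection only, with one extra check at 30 minutes for the first at-home injection.

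Median injection time with the device was 10 minutes in the Phase 1b study (Section 2.2.3.2). No scheduled post-injection check can therefore observe swelling beyond 24 hours or a reaction within 48 hours.

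**3. Diary end date**

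Dosing (synopsis, Section 6.1.1.4): 4 injections in Cycle 1, then 2 per cycle.

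- Before Cycle 9 Day 1: 4 + 7 × 2 = 18.
- First nine cycles: 4 + 8 × 2 = 20.
- Gap: 20 − 18 = 2 of 20 injections. If the Cycle 9 Day 1 injection is still recorded, the gap is 1 of 20 (Cycle 9 Day 15).

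At-home dosing is possible on Day 15 from Cycle 6. Of the four such days in nine cycles (Cycles 6, 7, 8 and 9), the schedule's end point covers three.

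**4. Table 19**

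- Cycle 1 SC injections: Days 1, 8, 15 and 22, so 4.
- Covered by the text of 8.4.7 and footnote x: 4 of 4.
- Covered by Table 19: Days 1, 8 and 15, so 3 of 4. Day 22 has no entry.
- Reference time: for Cycle 1 Day 1 the text counts from the start of administration. Table 19 lists end of injection, then 1 to 4 hours, without naming an origin. The two readings differ by the length of the injection, about 10 minutes at the Phase 1b median.

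**The case against.** The strongest reply is that the warning means only that nobody watches the diary between visits. It stands beside an instruction to call the doctor or nurse, a second instruction in capitals to seek care at once for severe symptoms, and the request to bring the pages in. The health resource questionnaire (Section 10.16.4) carries a similar disclaimer, so this may be standard wording carried over. That intention is plausible, but the sentence does not express it. The disclaimer suits the resource questionnaire, whose answers go to statisticians; it does not suit a diary meant for the investigator.

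A reader might infer that late ISRs reach the database mainly through the diary, and so that local tolerability will be understated. The documents do not support that:

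- Footnote w gives the diary a supporting role.
- All adverse events are collected from consent to 30 days after the last dose (footnote u).
- Open-ended questioning is the preferred detection method (Section 8.6.2), and events that did not worry the participant are collected by interview at the next visit (Section 10.3.1).
- Investigator assessment of local tolerability runs to the end-of-treatment visit.
- After the diary ends, these routes carry ISR collection alone.

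On the smaller items, Section 8 refers procedures and timing to the schedule of activities, where the row and footnote w agree with each other. Table 19 is titled a summary, the text covers Day 22, and Table 2 plans a 6-hour PK sample in the SC arm that day, so no practical loss from the missing entry is shown. This limits the weight of both conflicts; it does not remove them.

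**Conclusion.** The point stands as three internal contradictions in current text. The diary warning matters most, because participants and sites cannot act on both it and footnote w. The end-date conflict concerns 1 to 2 of 20 injections, and Table 19 omits 1 of 4 Cycle 1 injections and a reference time; both are minor.

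Under-capture is a risk confined to mild or moderate reactions appearing after the on-site check, since the form already directs severe symptoms to direct contact. Its size cannot be derived from the protocol: it depends on how participants and sites read the sentence, and on how much interview at visits recovers. It reaches only a descriptive, SC-only secondary endpoint and the AESI of Grade 2 or higher ISRs. The co-primary analyses, the key secondary hierarchy, the sample size and the type I error rate are untouched.

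**What to change.** 1. **Diary form (10.16.9).** Reword the warning to say that the diary is not monitored between visits but will be reviewed by the study team at the next visit. Keep the existing instruction to contact the nurse or doctor at once for severe symptoms or concerns.
2. **Diary end point.** Reconcile the schedule row, footnote w, Section 6.4.1 and Table 5 so that all state the same end, and say whether the injection given on the last diary day is recorded.
3. **Table 19.** Reconcile it with the text of 8.4.7 and footnote x for Cycle 1 Day 22, and name the reference time (start or end of injection) for each set of checks.

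The cost is a new version of a version-controlled form and a routine ethics submission, plus a few words in the protocol. No visit or analysis needs to be added: participants already bring the pages to the site.

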10.17 APPENDIX 17: IADL AND ADL QUESTIONNAIRES

INSTRUMENTAL ACTIVITIES OF DAILY LIVING SCALE (IADL) M.P. Lawton & E.M. Brody

A. Ability to use telephone		E. Laundry	
1. Operates telephone on own initiative; looks up and dials numbers, etc.	1	1. Does personal laundry completely	1
2. Dials a few well-known numbers	1	2. Launders small items; rinses stockings, etc.	1
3. Answers telephone but does not dial	1	3. All laundry must be done by others.	0
4. Does not use telephone at all.	0		
B. Shopping		F. Mode of Transportation	
1. Takes care of all shopping needs independently	1	1. Travels independently on public transportation or drives own car.	1
2. Shops independently for small purchases	0	2. Arranges own travel via taxi, but does not otherwise use public transportation.	1
3. Needs to be accompanied on any shopping trip.	0	3. Travels on public transportation when accompanied by another.	1
4. Completely unable to shop.	0	4. Travel limited to taxi or automobile with assistance of another.	0
C. Food Preparation		G. Responsibility for own medications	
1. Plans, prepares and serves adequate meals independently	1	5. Does not travel at all.	0
2. Prepares adequate meals if supplied with ingredients	0	H. Ability to Handle Finances	
3. Heats, serves and prepares meals or prepares meals but does not maintain adequate diet.	0	1. Manages financial matters independently (budgets, writes checks, pays rent, bills goes to bank), collects and keeps track of income.	1
4. Needs to have meals prepared and served.	0	2. Manages day-to-day purchases, but needs help with banking, major purchases, etc.	1
D. Housekeeping		3. Incapable of handling money.	0
1. Maintains house alone or with occasional assistance (e.g. "heavy work domestic help")	1		
2. Performs light daily tasks such as dish-washing, bed making	1		
3. Performs light daily tasks but cannot maintain acceptable level of cleanliness.	1		
4. Needs help with all home maintenance tasks.	1		
5. Does not participate in any housekeeping tasks.	0		

Source: Lawton, M.P., and Brody, E.M. "Assessment of older people: Self-maintaining and instrumental activities of daily living." Gerontologist 9:179-186, (1969).

Copyright (c) The Gerontological Society of America. Used by permission of the Publisher.

Katz Index of Independence in Activities of Daily Living

10.18 APPENDIX 18: ABBREVIATIONS AND DEFINITIONS

ADA:	anti-drug antibodies
ADE:	adverse device effect
ADL:	index of independence in activities of daily living
AE:	adverse event
AESI:	adverse event of special interest
ALT:	alanine aminotransferase
ANC:	absolute neutrophil count
anti-HBc:	antibody to hepatitis B core antigen
anti-HBs:	antibody to hepatitis B surface antigen
AST:	aspartate aminotransferase
AUC:	area under the curve
AUC _{1week} :	area under the plasma concentration time curve over the first week
AUC _{2weeks} :	area under the plasma concentration time curve over two weeks
AxMP:	auxiliary medicinal product
BM:	bone marrow
CI:	confidence interval
CID:	clinically important difference
C _{max} :	maximum concentration
CR:	complete response
C _{trough} :	observed concentration before dosing
CV:	coefficient of variation
CYP1A2:	cytochrome P450 family 1 subfamily A member 2
DLT:	dose limiting toxicity
DMC:	Data Monitoring Committee
DOE:	duration of response
EC:	ethics committee
ECG:	electrocardiogram
eCRF:	electronic case report form
eGFR:	estimated glomerular filtration rate
EMA:	European Medicines Agency
EORTC QLQ-C30:	European Organization for Research and Treatment of Cancer Quality of Life Questionnaire-Core 30
EORTC QLQ-MY20:	European Organization for Research and Treatment of Cancer Quality of Life Questionnaire- Myeloma Module 20
EOT:	end of treatment
ePRO:	electronic patient-reported outcome
EQ-5D-5L:	the European Quality of Life Group Questionnaire with 5 Dimensions and 5 Levels
EU:	European Union
FCBP:	female of childbearing potential
FDA:	Food and Drug Administration
FISH:	fluorescent in situ hybridization
FLC:	free light chain

G-CSF:	granulocyte-colony stimulating factor
GLP:	good laboratory practice
GvHD:	graft versus host disease
HA:	health authority
HBC:	hepatitis C virus
HBV:	hepatitis B virus
HCP:	health care professional
HIV:	human immunodeficiency virus
HR:	hazard ratio
HRUPQ:	health resource utilization and productivity questionnaire
IADL:	instrumental activities of daily living
IB:	Investigator's brochure
ICF:	informed consent form
IEC:	Independent Ethics Committee
IMP:	investigational medicinal product
IMWG:	international myeloma working group
IR:	infusion reaction
IRB:	Institutional Review Boards
IRC:	Independent Review Committee
IRT:	interactive response technology
IsaPd:	isatuximab in combination with pomalidomide and dexamethasone
ISRs:	injection site reactions
ITT:	intent-to-treat
IV:	intravenous
LPI:	last patient in
MDRD:	modification of diet in renal disease
MM:	multiple myeloma
MR:	minimal response
MRD:	minimal residual disease
MRI:	magnetic resonance imaging
MTD:	maximal tolerated dose
NCI CTCAE:	National Cancer Institute, Common Terminology Criteria for Adverse Events
NK:	natural killer
NMPA:	National Medical Products Administration
OBDS:	on body delivery system
ORR:	overall response rate
OS:	overall survival
PAT:	patient's assessment of treatment
PCSA:	potentially clinically significant abnormality
Pd:	pomalidomide and dexamethasone
PD:	progressive disease
PDy:	pharmacodynamic
PEQ:	patient expectation questionnaire
PEQ-BL:	patient expectations questionnaire at baseline
PESQ:	patient experience and satisfaction questionnaire
PESQ-EOT:	patient experience and satisfaction end of treatment questionnaire

PESQ-FU:	patient experience and satisfaction follow-up questionnaire
PET-CT:	positron emission tomography- Computed tomography
PFS:	progression free survival
PI:	proteasome inhibitor
PK:	pharmacokinetic
PML:	progressive multifocal leukoencephalopathy
PO:	per os
PP-PK:	per protocol PK
PR:	partial response
PRO:	patient-reported outcome
Q2W:	every 2 weeks
QTL:	quality tolerance limit
QWx4:	every week for 4 weeks
RP2D:	recommended Phase 2 dose
RRMM:	relapsed/refractory multiple myeloma
SADE:	serious adverse device effect
SAE:	serious adverse event
SAP:	statistical analysis plan
SC:	subcutaneous
SC-IP:	subcutaneous route using an infusion pump
SC-OBDS:	subcutaneous on body delivery system
sCR:	stringent complete response
SmPC:	summary of product characteristics
SoA:	schedule of activities
SPD:	sum of the products of the maximal perpendicular diameters of measured lesions
SUSAR:	suspected unexpected serious adverse reaction
TEAE:	treatment emergent adverse event
TT1R:	time to first response
TTBR:	time to best response
TTR:	time-to-response
ULN:	upper limit of normal
USADE:	unanticipated serious adverse device effect
VAS:	visual analogue scale
VGPR:	very good partial response

